17.6.4. Adverse Events

The Medical Dictionary for Regulatory Activities (MedDRA) will be used to code AEs.

An AE (classified by preferred term) that started on or after the date of the first dose of the study drug will be considered a TEAE if it was not present prior to the first dose of study drug, or was present prior to the first dose of study drug but increased in intensity during the treatment period. If more than 1 AE is reported prior to the first dose of study drug and coded to the same

preferred term, then the AE with the greatest intensity will be used as the benchmark for comparison to the AEs occurring during the treatment period which were also coded to that preferred term. Any AE present prior to the first dose of study drug that increases in intensity during the treatment period will be re-entered with a new start date of the date of increased intensity.

Descriptive statistics (the number and percentage) for subjects reporting TEAEs in each treatment arm will be tabulated by system organ class and preferred term; by system organ class, preferred term, and severity; and by system organ class, preferred term, and relationship to study drug. If more than 1 AE is coded to the same preferred term for the same subject, the subject will be counted only once for that preferred term using the most severe and most related occurrence for the summarization by severity and by relationship to the study drug.

Listings will be presented for subjects with SAEs, subjects with AEs leading to discontinuation of study or study drug, and subjects who die (if any).

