#### **4.6.1.2. Intensity of Adverse Events**

Intensity (or severity) of AEs will be graded as “Mild”, “Moderate” or “Severe”. For AEs with missing severity, the most severe assessment will be imputed for analyses, following worst case principle.

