### **7.8.2. Adverse Events**

All AE summary tables will include only TEAEs, unless otherwise specified.

AEs will be summarized by SOC and PT. A subject will only be counted once per SOC and PT.

For AEs by severity grade (mild, moderate, severe), if a subject has multiple events occurring in the same SOC or same PT, then the event with the maximum intensity (ie, severe) will be counted.

For AEs by relationship to study drug, if a subject has multiple events occurring in the same SOC or same PT, the event with the highest association (ie, related) to study drug will be summarized.

AEs will be presented in decreasing order of the incidences at SOC level and within each SOC, in decreasing order of the incidences at the PT level.

An overall summary of AE and AE related to study drug will be presented and will include:

- Total number of TEAEs reported
- Total number of TEAEs reported by severity
- Total number of AEs of special interest
- Subjects with any TEAE
- Subjects with any special interest AE
- Subjects with any serious TEAE
- Subjects with any severe TEAE

- Subjects with no severe TEAEs, but at least one moderate TEAE
- Subjects with no severe TEAEs, but at least one mild TEAE
- Subjects with any TEAEs leading to drug interruption/withdrawn
- Subjects with any TEAEs leading to study discontinuation
- Subjects with any TEAEs resulting in death

The following summary tables will be presented by SOC and PT:

- All TEAEs
- TEAEs by severity
- TEAEs by relationship to study drug
- All non-study drug related TEAEs
- All study drug related TEAEs
- Study drug related TEAEs by severity
- Serious TEAEs
- Serious study drug related TEAEs
- Duration of study drug related TEAEs (<14 days, 14 – 21 days and >21 days)
- TEAEs leading to drug interruption/withdrawn
- Study drug related TEAEs leading to drug interruption/withdrawn
- TEAEs leading to study discontinuation
- Study drug related TEAE leading to study discontinuation
- TEAEs resulting in death
- Study drug related TEAEs resulting in death
- AEs of special interest

Serious and most common non-serious TEAE by order of frequency (Most frequent, 2nd most frequent, and 3rd most frequent) will be summarized by PT. Most common non-serious AEs are any preferred term that at least 5% of the subjects reported at least once.

The following listings will be presented by subject:

- All AEs
- Serious AEs
- AEs resulting in drug interruption/withdrawn

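### The overview row for mild adverse events does not exclude moderate ones, so a subject with both grades and no severe event is counted in two severity rows

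*SAP*

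**What the plan says.** SAP 7.8.2 lists the contents of an overall summary of TEAEs, to be produced for all events and for events related to study drug. SAP 7.8 says that safety data are presented by treatment arm and by region. Three consecutive rows of the summary classify subjects by severity:

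- The severe row is "Subjects with any severe TEAE".
- The moderate row is "Subjects with no severe TEAEs, but at least one moderate TEAE".
- The mild row is "Subjects with no severe TEAEs, but at least one mild TEAE".

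The same list has a row for subjects with any TEAE.

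Three other rules bear on the point.

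- **Grades.** SAP 4.6.1.2 uses three: "Intensity (or severity) of AEs will be graded as “Mild”, “Moderate” or “Severe". It adds: "For AEs with missing severity, the most severe assessment will be imputed for analyses". Every TEAE therefore carries a grade in the analysis.
- **Counting within a term.** For the severity tables, where one subject has several events within one SOC or PT, SAP 7.8.2 says that "the event with the maximum intensity (ie, severe) will be counted". Protocol 17.6.4 has a similar rule for a single preferred term: "the subject will be counted only once for that preferred term using the most severe and most related occurrence".
- **Shells.** SAP section 11 places the table layouts in SAP Module 2, which is not among the documents available.

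**The concern.** The three rows read as a split of subjects by their worst grade. The moderate row excludes the one grade above it. The mild row has two grades above it and excludes only the higher.

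As written, the mild row answers no clear question. It is not the number of subjects with any mild event, because those who also had a severe event are removed. It is not the number whose worst event was mild, because those who also had a moderate event stay in.

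Safety by injection technique is the secondary objective (Protocol 9.2, SAP 2.2), and this summary gives the overview of it by arm. The excess in the mild row grows with the number of subjects who have both moderate and mild events. An arm with more moderate reactions could therefore also show a larger mild row, which makes arms harder to compare on that line.

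**Working it through.** **Step 1: apply the row definitions.** A subject may or may not have a mild, a moderate and a severe TEAE. That gives 8 combinations, 7 of them with at least one TEAE.

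| Mild | Moderate | Severe | Severe row | Moderate row | Mild row as written | Mild row if moderate is also excluded |
|---|---|---|---|---|---|---|
| no | no | no | 0 | 0 | 0 | 0 |
| no | no | yes | 1 | 0 | 0 | 0 |
| no | yes | no | 0 | 1 | 0 | 0 |
| no | yes | yes | 1 | 0 | 0 | 0 |
| yes | no | no | 0 | 0 | 1 | 1 |
| yes | no | yes | 1 | 0 | 0 | 0 |
| yes | yes | no | 0 | **1** | **1** | 0 |
| yes | yes | yes | 1 | 0 | 0 | 0 |

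As written, 6 of the 7 combinations with any TEAE fall in exactly one row. One, mild plus moderate without severe, falls in two. With moderate also excluded, all 7 fall in exactly one row, and the three rows add to the any-TEAE row.

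**Step 2: size of the excess.** The excess in the mild row equals the number of subjects with no severe TEAE who have both a moderate and a mild one:

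excess = N × (1 − s) × m × q

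- N is the number of subjects per arm. SAP 3.1 plans 6 per region per arm, so 6 + 6 = 12.
- s is the proportion with a severe TEAE. Assumed 0.
- m is the proportion of the others with a moderate TEAE. Assumed 10% to 40%.
- q is the proportion of those moderate subjects who also have a mild TEAE. Assumed 50% to 100%.

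The documents give no values for s, m or q.

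- Low end: 12 × 0.10 × 0.50 = 0.6 subjects.
- High end: 12 × 0.40 × 1.00 = 4.8 subjects.
- With q = 0 the excess is 0 for any m.
- With s = 5% the range becomes 12 × 0.95 × 0.05 = 0.57 to 12 × 0.95 × 0.40 = 4.56.

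**Step 3: one worked arm.** Take N = 12, s = 0, m = 20%, and assume that 80% of subjects without a moderate event have a mild one.

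- Moderate row: 12 × 0.20 = 2.4.
- Worst event mild: 12 × 0.80 × 0.80 = 7.68.
- Any TEAE: 2.4 + 7.68 = 10.08.
- Mild row as written: 7.68 + 2.4 × 0.5 = 8.88 at q = 50%, and 7.68 + 2.4 = 10.08 at q = 100%.
- Sum of the severity rows: 2.4 + 8.88 = 11.28 to 2.4 + 10.08 = 12.48, against 10.08 subjects with any TEAE.

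**Step 4: weight of one subject.** One subject counted twice adds 1/12 = 8.3 percentage points to the mild row for an arm, or 1/6 = 16.7 points within one region of an arm.

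**The case against.** The case for leaving this alone has real substance.

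- **The right number can be recovered.** Every TEAE has a grade, so the number of subjects whose worst event was mild is the any-TEAE row minus the severe row minus the moderate row. All three are correctly defined in the same table. In the worked arm, 10.08 − 0 − 2.4 = 7.68. This stands, and it limits the harm, but a reader must first notice that the printed row is something else.
- **The intent is inferred.** The SAP does not say that the rows are mutually exclusive or that they add to the any-TEAE row, and the Module 2 shell may already be right. This also stands. Still, nothing in the available text redefines the row, and a shell that differed would conflict with the SAP.
- **Little rests on it.** The study is open-label and exploratory without a control group, and no test or decision rule uses the row. Agreed.

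A reader might also infer more than the documents support.

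- *The row contradicts the maximum-intensity rule in the same section.* It does not. That rule covers multiple events within the same SOC or PT, and the protocol's rule covers a single preferred term. Neither governs a subject-level overview row.
- *Every subject with a moderate event is counted twice.* Only those who also have a mild event and no severe one are. A subject with moderate events alone is not in the mild row.
- *The overlap is sure to be common.* Protocol 8.3 gives Phase 2b treatment-related rates of 75.1% for bruising and 59.3% for pain, so at least 75.1 + 59.3 − 100 = 34.4% of subjects had both. That shows two types of event in one subject, not two grades. If both were mild, or both moderate, the rows would not overlap.

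**Conclusion.** The point holds as a minor definitional error. Followed literally, SAP 7.8.2 counts a subject with no severe TEAE but both a moderate and a mild TEAE in two severity rows. The logic rests on the row wording alone and needs no assumption.

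The size does need assumptions. It is about 0.6 to 4.8 subjects per arm of 12 if nobody has a severe event, 10% to 40% have a moderate one, and half to all of those also have a mild one. It is zero if no subject has mixed grades. None of these rates comes from the documents.

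Only the mild row is wrong, in the overview for all TEAEs and in the one for related TEAEs. The severe and moderate rows, the event counts by severity, the severity tables by SOC and PT, and the listings are unaffected. Severe and moderate reactions are not under-reported.

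**What to change.** In the mild row of the overview in SAP 7.8.2, add *or moderate* after *no severe*, so that the row counts subjects whose worst TEAE was mild. Check the Module 2 shell and make it agree. The three rows then add to the any-TEAE row, which gives programmers a simple check.

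If overlap is intended, keep the row and footnote the table to say that the severity rows are not mutually exclusive.

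The cost is one line in the SAP and one in the shell, with no new data and no change to any other analysis.

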8.4. Rationale

The results from the Phase 2b EFP study (EN3835-201) further suggested that CCH 0.84 mg per treatment area (quadrant) is an effective treatment of EFP based on improvement in the severity of cellulite as determined by the Investigator and the subject. There were no safety concerns following 0.84 mg per treatment area in the treatment of EFP. Safety findings from the Phase 2b EFP and ongoing Phase 3 studies are similar to that observed in previous clinical studies with CCH in the treatment of EFP and XIAFLEX in the treatment of Dupuytren's contracture and Peyronie's disease, in that the majority of AEs occurred at the site of injection and resolved before the next scheduled treatment. The immunogenicity profile of CCH in the Phase 2b EFP study is similar in previous studies and programs.

Input from published literature, as well as input from aesthetic medicine specialists, indicated a desire to investigate multiple injection/dosing techniques of CCH for EFP treatment and to examine the role 3-dimensional (3-D) imaging paradigms can play in visualizing the treatment effect of CCH on EFP.

This clinical study protocol will explore these different treatment and outcome assessment paradigm possibilities. Learnings from this study could assist both the sponsor and the aesthetic medicine community in designing future clinical studies.

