17. STATISTICAL CONSIDERATIONS AND METHODS

17.1. Determination of Sample Size

No sample size estimation was done for this study.

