### **2.2. Secondary Objective**

The secondary objective of this study is to assess the safety of CCH when administered using different injection techniques in subjects with EFP.

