## **3. STUDY DESIGN AND MEASURES**

### **3.1. Study Design**

This is a Phase 2a, open-label, multicenter, exploratory study to evaluate the safety and effectiveness of different injection techniques of CCH for the treatment of adult women with EFP. This study will be performed at approximately 5 sites in the United States (US).

Subjects having the evidence of cellulite in 2 buttocks or 2 thighs (treatment area) at the Screening Visit will be enrolled if they satisfy the criteria below:

- Have a CR-PCSS score of 2 (mild), 3 (moderate) or 4 (severe) as reported by the Investigator in 2 treatment areas (two thighs or two buttocks)
- Have at least 2 dimples from each treatment area that:
  - are isolated and separated by at least 5 cm from any other dimples

- score 2 or 3 on the Hexsel depression scale
- have dimple width: length ratio  $\geq 0.5$

If both buttocks and both thighs meet entry criteria for a single subject, then the thighs will be treated. No subject will be treated for EFP in both the buttocks and the thighs during this study.

The study will enroll approximately 60 subjects; 30 subjects with 2 eligible buttocks (to be dosed in the buttocks) and 30 subjects with 2 eligible thighs (to be dosed in the thighs). The 30 subjects in each treatment region (buttocks or thighs) will be assigned sequentially to 1 of 5 injection technique treatment arms on Day 1 (ie, 6 subjects per region per treatment arm). No control groups will be employed. Subjects who discontinue from the study will not be replaced.

Subjects who complete the study will participate for approximately 92 days including a 21-day of screening period, a 43-day treatment period and a 28-day follow-up period. Subjects will receive the study injections on Days 1, 22, and 43. Additional scheduled assessments will be performed on Days 4, 8, 15, and 71.

[Table 1](#) below describes the schedule of events and assessments performed during screening, treatment visits, and assessment visits.

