### 3.10. Bruise Analysis

The IAT will trace the bruise on the Day 4 image in addition to an area of normal skin. The bruise tracing and normal tissue tracing will be transposed onto the Day 1-Pre Marking, Day 8, and Day 15 images.

A pair of numerical values of the mean lab color (number) value of bruised area and normal skin color value will be collected from the 3-D photographs at each imaging evaluation visit for bruising.

Bruise analysis will consist of two L\*A\*B\* color measurements. L\*A\*B\* color values will be measured within the bruised tissue and normal tissue area of interest (AOI).

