Baseline for Hexsel Depression Depth Scale	The investigator assessment performed at Screening for each treatment area will be considered as Baseline.
Duration of Exposure at Each Visit	Date/Time of Last Injection – Date/Time of First Injection
Duration of AE	AE end date – AE start date + 1
AE Onset Day	AE start date - Date of first injection + 1

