## **7.8. Safety Analyses**

Safety data will be summarized by treatment arm and by treatment region (ie, Buttocks, Thighs, and Overall) using the Safety Population.

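### The only by-arm summary of how long drug-related reactions last puts everything under 14 days in one bin, so differences between techniques within the first 13 days are largely hidden in that table

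*SAP*

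**What the plan says.** SAP 7.8.2 lists, among the tables by system organ class and preferred term, "Duration of study drug related TEAEs (<14 days, 14 – 21 days and >21 days". SAP 7.8 sets the layout: "Safety data will be summarized by treatment arm and by treatment region (ie, Buttocks, Thighs, and Overall) using the Safety Population". SAP Table 12 defines the underlying variable as "AE end date – AE start date + 1", a count of whole days. The SAP text names no mean, median, quartiles or time to resolution for adverse-event duration, and Protocol 17.6.4 has no duration analysis.

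The table serves the secondary objective, to "assess the safety of CCH when administered using different injection techniques in subjects with EFP". On expected duration, Protocol 8.4 says of earlier studies that "the majority of AEs occurred at the site of injection and resolved before the next scheduled treatment". It gives no median or spread.

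Bruising has a separate early assessment. SAP 3.10 traces the bruise on the Day 4 image and states: "The bruise tracing and normal tissue tracing will be transposed onto the Day 1-Pre Marking, Day 8, and Day 15 images". SAP 7.8.7 summarises the colour difference from normal skin at those visits by treatment area and arm.

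**The concern.** Treatments are 21 days apart, and most reactions are expected to clear within that interval. The first bin takes in days 1 to 13 of it. If one technique's bruising or pain typically clears in 4 days and another's in 8, nearly all subjects in both arms land in the same cell.

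This matters because local reactions are expected in most subjects. In the Phase 2b study (Protocol 8.3), 75.1% had injection-site bruising and 59.3% had pain. With 12 subjects per arm, incidence alone may not separate techniques. Duration is one of the few safety measures that might, and the plan discards the day-level detail when it tabulates by arm.

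**Working it through.** **Inputs from the documents.** SAP 3.1 gives "6 subjects per region per treatment arm", so 6 × 2 regions = 12 per arm and 12 × 5 arms = 60 in total, which agrees with the planned size. There is no powered figure to reproduce; Protocol 17.1 states: "No sample size estimation was done for this study". The cut-points are 14 and 21 days.

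**Assumptions, not in the documents.** One duration per subject, lognormal, log SD 0.4 to 0.8, rounded to whole days. A two-sided 5% rank-sum test serves only as a gauge of information lost; the SAP plans no such test.

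**Share in the first bin.** P(duration < 14 days) = Φ[(ln 13.5 − ln median) / log SD].
- Median 4, log SD 0.6: Φ(1.216 / 0.6) = Φ(2.03) = 97.9%.
- Median 8, log SD 0.6: Φ(0.523 / 0.6) = Φ(0.87) = 80.8%.
- At log SD 0.4 the two shares are 99.9% and 90.5%; at 0.8 they are 93.6% and 74.3%.

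**Chance of detecting a doubling of the median, 12 v 12 subjects (1,500 simulated trials), days / three bins:**

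| Medians (days) | log SD 0.4 | log SD 0.6 | log SD 0.8 |
|---|---|---|---|
| 3 v 6 | 0.98 / 0.00 | 0.70 / 0.02 | 0.48 / 0.07 |
| 4 v 8 | 0.98 / 0.02 | 0.73 / 0.15 | 0.51 / 0.19 |
| 5 v 10 | 0.98 / 0.26 | 0.73 / 0.33 | 0.49 / 0.27 |
| 7 v 14 | 0.98 / 0.81 | 0.74 / 0.55 | 0.48 / 0.36 |

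For 3 v 6 days, every subject in both arms falls in one bin in 77%, 31% and 9% of trials. For 4 v 8 days within one region (6 v 6), the figures are 0.69 / 0.00, 0.37 / 0.01 and 0.23 / 0.03.

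**Longer durations.** With medians 10 v 15 or 10 v 20 days, log SD 0.5 to 0.8 and 9 or 12 subjects per arm, days beat bins by only about 1 to 9 percentage points. A tighter spread would make the loss somewhat larger.

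**Which terms have enough events.** Phase 2b rates × 12 subjects: bruising 0.751 × 12 = 9.0; pain 0.593 × 12 = 7.1; nodule 0.143 × 12 = 1.7; pruritus 0.111 × 12 = 1.3; swelling 0.074 × 12 = 0.9; induration 0.058 × 12 = 0.7. That study treated one area per subject and this one treats two, so the rates may be higher here.

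**The case against.** A reader might infer that early differences cannot show anywhere in the results. The documents do not support that. Bruise colour is summarised by arm at Days 4, 8 and 15, SAP 6.1 lists all derived variables by subject, and the bins keep much of the signal once one arm's durations run past day 13. What survives is narrower. Colour is not duration. The images stop at Day 15, so they cover only the first treatment. Pain, nodules, pruritus, swelling, induration and erythema are not covered. Listings leave the reader to build an unplanned summary.

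A reader might also infer that a planned comparison between techniques loses power. None is planned: the adverse-event tables are descriptive, the stated alpha is for efficacy parameters, and arms are assigned sequentially rather than randomised.

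Other points for the plan:
- **The bins have a basis.** The 21-day cut matches the treatment interval and answers whether reactions outlast it. That stands, and is why the table should stay.
- **Day-level precision is limited.** Events are elicited by asking what happened since the last visit. After Day 1 the gaps between visits are 3, 4, 7 and 7 days; after the Day 22 and Day 43 injections the next scheduled visits are 21 and 28 days later. End dates for those two courses rest partly on recall, so the simulated power on days is optimistic.
- **Few terms have enough events.** At the Phase 2b rates, only bruising and perhaps pain support a median by arm.
- **Table layouts are in SAP Module 2, which was not available**, and SAP 6.1 says in general that continuous data get descriptive statistics. The finding is therefore about what the SAP text names; its specific entry for duration is the three bins.

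**Conclusion.** The point holds as a modest one. Duration is derived in days, but the only by-arm summary the SAP text names pools days 1 to 13, where the protocol's own rationale suggests many reactions may end.

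The size depends entirely on an assumed distribution. If medians are well under 14 days (3 v 6 or 4 v 8), about 32 to 98 points of illustrative power are lost at 12 per arm. At 7 v 14 days the loss is about 12 to 20 points. If both medians are 10 days or more, it is about 1 to 9 points at log SD 0.5 to 0.8. These figures assume exact end dates and one event in every subject, or in 9 of 12 for the lower count used in the last range.

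Nothing in the plan is contradictory or invalid here. The change is a cheap gain for the secondary objective, and any result stays descriptive.

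**What to change.** Keep the three-bin table. In SAP 7.8.2 add one descriptive table of duration in days by arm, pooled over regions, for injection-site bruising, injection-site pain and any other injection-site term with enough events. Report n, median and quartiles by Kaplan-Meier, and range.

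State two rules that the duration table now lacks:
- **Repeat events:** use the longest event per subject and preferred term. SAP 7.8.2 has rules for multiple events only for counting, severity and relationship.
- **Ongoing events:** censor at last contact. Protocol 14.5.1 ends follow-up at resolution or 28 days after the last visit, so the longest event may have no end date. Dropping it would bias the median downwards.

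Also show separately the events that start after the Day 1 injection and before the Day 22 injection. The Day 4, 8 and 15 visits make those end dates more reliable.

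Pairwise confidence intervals are not needed: five arms give 5 × 4 / 2 = 10 pairs per term, without randomisation.

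The cost is a few lines of SAP text and one table from a variable already derived. The downside is limited precision at 12 or fewer subjects per arm, with some end dates based on recall.
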